5.4.5.5 Management of infusion-related reactions for combination therapy arms

Pembrolizumab

Pembrolizumab may cause severe or life-threatening infusion-reactions, including severe hypersensitivity or anaphylaxis. Signs and symptoms usually develop during or shortly after drug infusion and generally resolve completely within 24 hours of completion of infusion. For ≤Grade 2 IRRs, interrupt or slow the rate of infusion.³² For ≥Grade 3 IRRs, stop infusion and permanently discontinue pembrolizumab.³²

Ipilimumab

Severe infusion reactions can occur with ipilimumab. For ≤Grade 2 IRRs, interrupt or slow the rate of infusion.³³ For ≥Grade 3 IRRs, stop infusion and permanently discontinue ipilimumab.³³

5.4.6 Treatment Compliance

The Investigator or other study site personnel under the direction of the Investigator will be responsible for study drug administration and recording dosing information in source documents.

Patient compliance will be assessed by the site using drug dispensing and infusion logs, and progress notes about dose reductions/interruptions. The CRF will capture infusion details and reasons for changes in dose level (eg, a new record completed each time dose level changes, including periods where no dose was taken, and the reason for a dose level change).

5.4.7 Storage and Accountability

ANV419 will be sent at -20° C under a temperature-controlled shipment and stored in a secure, limited access storage area at -20° C ($\pm 5^{\circ}$ C) until use. The assigned personnel should ensure that the study drug is stored in accordance with the environmental conditions (temperature, light, humidity) as determined by the Sponsor. If concerns regarding the quality or appearance of the study drug arise, the study drug should not be dispensed and the Sponsor or designee should be contacted immediately.

For details regarding the storage of pembrolizumab and ipilimumab, please see the approved package insert of each.

Records will be maintained indicating the receipt and dispensation of all study drug supplies. At the conclusion of the study, the clinical site will be responsible for final drug accountability and destruction.

5.5 Prior and Concomitant Medications and/or Procedures

5.5.1 Excluded Medications and/or Procedures

The following medications and procedures are prohibited during the Screening and study:

- Any investigational agent (including investigational device) other than ANV419, pembrolizumab, and ipilimumab;
- Antineoplastic systemic chemotherapy or biological therapy;
- Immunotherapy not specified in this Protocol;
- Radiation therapy;
 - Note: Radiation therapy to a symptomatic solitary lesion or to the brain may be allowed after discussion between the Investigator and Sponsor.
- Systemic glucocorticoids for any purpose other than to modulate symptoms from an event of clinical interest of suspected immunologic etiology;
 - Note: The use of physiologic doses of corticosteroids may be approved after consultation with the Sponsor.
- Live vaccines administered within 30 days of planned start of study drug; and
 - Note: Seasonal influenza vaccines for injection are generally inactivated flu vaccines and are permitted; however, intranasal influenza vaccines (eg, Flu-Mist) are live attenuated vaccines and are prohibited.
- Local surgery resulting from disease progression is prohibited; however, if indicated for palliative measure and after Investigator approval, local surgery may be permitted after the Patients who, in the opinion of the Investigator, require the use of any aforementioned treatments for clinical management should be removed from the study.

5.5.2 Allowed Medications and/or Procedures

All treatments that the Investigator considers necessary for a patient's welfare may be administered at the discretion of the Investigator in keeping with the community standards of medical care.

Drug-drug interaction studies have not been conducted with ANV419; however, ANV419 may cause the release of cytokines that may suppress CYP450 enzymes. If a patient is using any concomitant medications known to be sensitive substrates of CYP450 in this study, safety events should be closely monitored. See Appendix E for examples of sensitive clinical substrates for CYP450-mediated metabolism.

5.5.3 Documentation of Prior and Concomitant Medication Use

The use of prior or concomitant medications will be recorded from 28 days prior to Cycle 1 Day 1 to the Safety Follow-Up Visit up to 90 days after last dose of study drug or the start date of a new cancer regimen, whichever is shorter, except for concomitant medications related to cancer treatment, for which lifetime history prior to entering the study will be recorded.

6 STUDY PROCEDURES

All study procedures will follow the Schedule of Procedures, see Appendix A.

6.1 Tumor Measurements

Tumor measurements will be performed as indicated in Appendix A.

Tumors will be assessed based on RECIST (see Appendix C) and iRECIST (see Appendix D).

Baseline disease assessment will include radiographic tumor measurements using CT imaging of the chest, abdomen, pelvis, or any other areas with suspected disease involvement and CT or magnetic resonance imaging of the brain during Screening.

On-study scans should be performed

using the same modality as used for baseline imaging until progressive disease per RECIST and iRECIST, withdrawal of consent, or initiation of a new anticancer therapy. Brain imaging is only to be repeated for patients with history, ongoing, or suspicion of central nervous system involvement.

Eastern Cooperative Oncology Group Performance Status

ECOG Performance Status will be assessed as indicated in Appendix A using the ECOG scale (see Appendix G).

6.3 Quality of Life Evaluation

Quality of Life (QoL) evaluations (EQ-5D-5L and QLQ-C30) are to be performed for clinical benefit assessment at baseline and every 12 weeks after Cycle 1 Day 1 in combination arms (Arms B and C).

6.4 Optional Tissue Biopsies

For patients consenting to biopsy, fresh tumor tissue will be collected at screening and then onstudy within ± 3 days of the imaging assessment and 7 days of the start of the next dosing cycle. Biopsy will be performed if the procedure is considered at low risk for the patient, clinically feasible and if the tumor is of sufficient size to be biopsied, otherwise, for baseline specimens, archived biopsy might be used if not older than 3 months at time of ICF signature. Any tissue that is suspected to contain tumor, including lymph nodes, may be biopsied.

Available archived biopsies will be collected in patients who do not consent to on study biopsy, provided the tumor tissue is not older than 3 months at time of ICF signature.

6.5 Pharmacokinetic Analyses

Serum samples for PK will be drawn as indicated in Appendix A.

If warranted for additional safety assessments, additional samples can be collected by the Investigator after discussion with the Sponsor. All samples will be sent to the central laboratory. Please refer to the laboratory manual for details.

PK parameters to be analyzed:

- Systemic clearance (CL) of ANV419;
- Volume of distribution at steady state (V_{ss}) of ANV419;
- Area under the concentration-time curve (AUC) of ANV419; and
- Maximum observed serum concentration (C_{max}) of ANV419.

6.6 Pharmacodynamic Analyses (Immuno-Profiling and Ki67 Analysis)

Blood samples for PD will be drawn as indicated in Appendix A.

All samples will be sent to the central laboratory. Please refer to the laboratory manual for details.

Immunophenotyping using flow cytometry has become the method of choice in identifying cells within blood samples and can therefore be used to monitor the mode of action of ANV419 as monotherapy or in combination with other treatments. Potential predictive markers of efficacy will also be explored.

Immunophenotyping markers may include, but will not be limited to, CD3, CD4, CD8, CD25, FoxP3, CD56, CD16, CD279, CD366, and Ki67.

6.7 Exploratory Serum Biomarker Analyses

Serum samples for biomarkers will be drawn as indicated in Appendix A.

If warranted for an additional PD assessment or if a PD visit is missed, an additional blood sample can be collected by the Investigator at a later visit after discussion with the Sponsor. All samples will be sent to the central laboratory. Please refer to the laboratory manual for details.

6.8 Peripheral Blood Mononuclear Cell and Cytokine Production Analyses

PBMC samples will be collected for all patients in the Monotherapy Dose Expansion part and Combination Dose Finding part. Samples will be drawn as indicated in Appendix A.

All samples will be sent to the central laboratory. Please refer to the laboratory manual for details.

The analysis of cytokines derived from peripheral blood stimulated immune cells will provide direct evidence about their functionality and potential for cytotoxic cell killing and ultimately reduction of tumor growth. The following markers will be analyzed in PBMC samples using flow cytometry or using the Isoplexis system, potentially after magnetic isolation of different cell populations and stimulation: cytokines including, but not limited to, Interferon γ , Tumor Necrosis Factor, IL-6, IL-2, and IL-10.

6.9 Tumor Mutational Burden and Circulating Tumor DNA Analyses

Sampling for circulating tumor DNA (ctDNA) analyses will occur for patients that agree to perform tumor biopsies at the timepoints indicated in Appendix A.

All samples will be sent to the central laboratory. Please refer to the laboratory manual for details.

In recent years, the analysis of tumor mutational burden was shown to correlate with higher immunogenicity of tumors, and a correlation with response to checkpoint inhibitor treatment has been proposed. ctDNA has been recently described as a predictive biomarker for pembrolizumab as a single agent in 25 different cancers and has been shown to identify patients with highly favorable survival.³⁹ Therefore, tumor mutational burden may be monitored through defined

commercial panels or through whole exome sequencing, and ctDNA in the blood may be analyzed for specific mutations defined in tumor biopsies.

6.10 Other Exploratory Biomarkers

Other potential exploratory biomarkers that may be measured include the following:

- Density and/or percentage of cell populations determined by immunohistochemistry (examples may include, but are not limited to, CD8, CD366 (TIM-3), CD19, CD45, Ki67, CD56, Immunoglobulin G1, FoxP3, CD3, CD127, CD25, CD279 (PD-1), CD4, NKG2D, CD16, Perforin, CD20, and tumor specific markers);
- Concentration of peripheral blood soluble biomarkers (examples include, but are not limited to, soluble CD25, soluble PD-1/PD-L1, and IL-6);
- Protein and RNA expression patterns in target cell populations and tissues outlined above using, but not limited to, CyTOF® and/or gene expression methods;
- Single nucleotide polymorphisms;
- T cell receptor repertoire;
- Epigenetic markers; and
- Isolated immune cells from patient PBMCs analyzed via functional assays.

While the goal of the biomarker assessments is to provide supportive data for the clinical study, there may be circumstances when a decision is made to stop a collection, or to not perform or discontinue an analysis due to either practical or strategic reasons (eg, inadequate sample number, issues related to the quality of the sample, issues related to the assay that preclude analysis, or impossibility to perform correlative analyses, etc). Therefore, depending on the results obtained during the study, sample collection and/or analysis may be omitted at the discretion of Sponsor.

6.11 Immunogenicity Analyses

Blood samples for anti-drug antibodies (ADA) will be drawn as indicated in Appendix A and analyzed at a central laboratory. Please refer to the laboratory manual for details. Additional samples will be taken in the case of an IRR or irAE to rule out involvement of ADA. ADA samples will be analyzed for anti-ANV419 antibodies, their cross-reactivity to human IL-2, and their capacity to neutralize ANV419 function in a cell-based assay. In case of a Grade 3 or higher IRR, irAE, or any other AE deemed clinically suspicious of an irAE as judged relevant by the SRC, all available ADA samples from the respective patient will be analyzed immediately.

The probability of inducing a clinically relevant anti-ANV419 immune response is considered to be moderate. The most important potential risk associated with an anti-ANV419 humoral immune response is neutralization of endogenous IL-2, as this might result in systemic activation of immune effector cells. However, no such response was observed to aldesleukin, and therefore, this risk for severe consequences is considered low. In conclusion, the overall immunogenicity risk in the context of oncology indications is considered low to moderate as the probability of an ADA response is moderate while the severity of possible consequences is considered to be low.

6.12 Serology

Serology assessments will be performed as indicated in Appendix A and will include the analytes presented in Appendix B.

6.13 Sample Labeling and Storage

Details regarding sample collection, preparation, handling, storage, and shipping instructions are provided in the Laboratory Manual.

6.13.1 Sample Labeling

Each sample will be clearly labeled with the following information:

- Protocol number;
- Subject ID;
- Visit;
- Sample name;
- Sampling time; and
- Scheduled sampling time point.

6.13.2 Sample Storage

Procedures for storage and shipment will be followed according to the Laboratory Manual. The samples can be destroyed by specific authorization from the Sponsor.

7 SAFETY ASSESSMENTS

7.1 Adverse Events

An AE is defined as any untoward medical occurrence in a clinical investigation patient administered a pharmaceutical product, which does not necessarily have a causal relationship with this treatment. An AE can therefore be any unfavorable and/or unintended sign (including an abnormal laboratory finding), symptom, or disease temporally associated with the use of an investigational medicinal product, whether or not related to the investigational medicinal product. All Aes, including observed or volunteered problems, complaints, or symptoms, are to be recorded on the appropriate eCRF.

Aes, which include clinical laboratory test variables, will be monitored and documented in accordance with NCI CTCAE version 5.0 from signing of informed consent until the Safety Follow-Up Visit up to 90 days after the last dose of study drug or the start of a new cancer regimen, whichever is shorter. Patients should be instructed to report any AE that they experience to the Investigator, whether or not they think the event is due to study drug. Beginning at signing of informed consent, Investigators should make an assessment for Aes at each visit and record the event on the appropriate AE eCRF.

Wherever possible, a specific disease or syndrome rather than individual associated signs and symptoms should be identified by the Investigator and recorded on the eCRF. However, if an observed or reported sign or symptom is not considered a component of a specific disease or syndrome by the Investigator, it should be recorded as a separate AE on the eCRF. Additionally, the condition that led to a medical or surgical procedure (eg, surgery, endoscopy, tooth extraction, or transfusion) should be recorded as an AE, not the procedure itself.

A complete medical history will be compiled for each patient. Any medical condition already present at Screening should be recorded as medical history and not be reported as an AE unless the medical condition or signs or symptoms present at baseline changes in severity, frequency, or seriousness at any time during the study. In this case, it should be reported as an AE.

Clinically significant abnormal laboratory or other examination (eg, electrocardiogram [ECG]) findings that are detected during the study or are present at the signing of informed consent and significantly worsen during the study should be reported as Aes, as described below. The Investigator will exercise his or her medical and scientific judgment in deciding whether an abnormal laboratory finding or other abnormal assessment is clinically significant. Clinically significant abnormal laboratory values occurring during the clinical study will be followed until repeat tests return to normal, stabilize, or are no longer clinically significant. Abnormal test results that are determined to be an error should not be reported as an AE. Laboratory abnormalities or other abnormal clinical findings (eg, ECG abnormalities) should be reported as an AE if any of the following are applicable:

- If an intervention is required as a result of the abnormality;
- If action taken with the study drug is required as a result of the abnormality; or
- Based on the clinical judgment of the Investigator.

7.1.1 Adverse (Drug) Reaction

All noxious and unintended responses to a medicinal product related to any dose should be considered an adverse drug reaction. "Responses" to a medicinal product means that a causal relationship between a medicinal product and an AE is at least a reasonable possibility, ie, the relationship cannot be ruled out.

7.1.2 Unexpected Adverse Drug Reaction

An Unexpected Adverse Drug Reaction is defined as an adverse reaction, the nature or severity of which is not consistent with the applicable product information. For ANV419, pembrolizumab, and ipilimumab, the reference safety information is included in Section 6 of the Investigator's Brochure currently in force. The reference safety information for ANV419 will be reviewed yearly and the periodicity of the review will be harmonized with the reporting period of the Development Safety Update Report where possible.

7.1.3 Assessment of Adverse Events by the Investigator

The severity of all Aes should be graded according to the NCI CTCAE version 5.0. For those AE terms not listed in the CTCAE, the following grading system should be used:

- CTCAE Grade 1: Mild; asymptomatic or mild symptoms; clinical or diagnostic observations only; intervention not indicated;
- CTCAE Grade 2: Moderate; minimal local or noninvasive intervention indicated; limiting age-appropriate instrumental activities of daily living;
- CTCAE Grade 3: Severe or medically significant but not immediately life-threatening; hospitalization or prolongation of hospitalization indicated; disabling; limiting self-care activities of daily living;
- CTCAE Grade 4: Life threatening consequences; urgent intervention indicated; and
- CTCAE Grade 5: Death related to the AE.

Causality assessment

The relationship of an AE to the administration of the study drug is to be assessed according to the following definitions:

No (unrelated, not related, unlikely to be related) – The time course between the administration of study drug and the occurrence or worsening of the AE rules out a causal relationship and another cause (concomitant drugs, therapies, complications, etc) is suspected; and

Yes (possibly, probably, or definitely related) – The time course between the administration of study drug and the occurrence or worsening of the AE is consistent with a causal relationship and no other cause (concomitant drugs, therapies, complications, etc) can be identified.

The definition implies a reasonable possibility of a causal relationship between the event and the study drug. This means that there are facts (evidence) or arguments to suggest a causal relationship.

The following factors should also be considered:

• The temporal sequence from study drug administration-

The event should occur after the study drug is given. The length of time from study drug exposure to event should be evaluated in the clinical context of the event.

• Underlying, concomitant, intercurrent diseases-

Each report should be evaluated in the context of the natural history and course of the disease being treated and any other disease the patient may have.

Concomitant drug-

The other drugs the patient is taking or the treatment the patient receives should be examined to determine whether any of them might be recognized to cause the event in question.

• Known response pattern for this class of study drug-

Clinical and/or preclinical data may indicate whether a particular response is likely to be a class effect.

• Exposure to physical and/or mental stresses-

The exposure to stress might induce adverse changes in the recipient and provide a logical and better explanation for the event.

• The pharmacology and pharmacokinetics of the study drug-

The known pharmacologic properties (absorption, distribution, metabolism, and excretion) of the study drug should be considered.

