4.3.1 Criteria for suspension of enrollment

In any case, the study will be paused and the Investigators, Institutional Review Board (IRB)/Independent Ethics Committee (IEC), regulatory agencies, and SRC will be promptly informed if any patient develops, in the dose expansion parts (Part 1 and Part 3), any of the following events assessed to be related to study drug by the Investigator and/or SRC:

- Life-threatening (Grade 4) toxicity that is unexpected and/or unmanageable (ie, does not resolve to Grade 3 or lower within 7 days)
- Death

The SRC will be urgently convened to review the safety data and make recommendations for potential changes in the study conduct (e.g. permanent discontinuation, dose reduction of a treatment in the combination arm or adaptation of the safety monitoring measures). If enrollment suspension is triggered due to an AE suspected to be related to ANV419, the enrollment in the

study will be paused. However, if the enrollment suspension is triggered due to a known toxicity of pembrolizumab or ipilimumab, or suspected synergistic toxicity in only one of the tested combination therapy arm, the monotherapy arm and the other combination therapy arm will still proceed if toxicity is not observed.

Should enrollment in the study or in one treatment arm be suspended, the study will not be restarted until all parties (SRC and Sponsor) have agreed to the course of action to be taken and the IRBs/IECs have been notified.

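### The two causality categories in Protocol 7.1.3 do not cover every adverse event, and they conflict with the standard set in 7.1.1

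*Protocol*

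**What the plan says.** Protocol 7.1.1 defines an adverse drug reaction broadly. It is enough that "a causal relationship between a medicinal product and an AE is at least a reasonable possibility, ie, the relationship cannot be ruled out".

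Protocol 7.1.3 gives the operational rating, with two options only:

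- The affirmative option is labelled "Yes (possibly, probably, or definitely related" and so expressly includes possible relationships. Its text requires that the time course fit a causal relationship and that "no other cause (concomitant drugs, therapies, complications, etc) can be identified".
- The negative option requires that the time course "rules out a causal relationship and another cause (concomitant drugs, therapies, complications, etc) is suspected".

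A sentence after the two definitions says that a reasonable possibility of causality is implied, meaning that "there are facts (evidence) or arguments to suggest a causal relationship". A list of factors to consider follows, including underlying disease and concomitant drugs.

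The rating is used in several places. Protocol 4.3.1 pauses the study in Parts 1 and 3 for "any of the following events assessed to be related to study drug by the Investigator and/or SRC", the events being certain Grade 4 toxicities and death. Protocol 8.2.6 summarizes TEAEs by relationship to study drug. SAP 3.8.1.1 tabulates ANV419-related TEAEs and ANV419-related serious TEAEs. SAP 3.8.1 defines a related TEAE as one with a reasonable causal relationship, and adds those whose causality assessment is missing.

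**The concern.** Finding another cause for an event does not show that the drug played no part. Section 7.1.1 accepts this; the text of *Yes* in 7.1.3 does not. An investigator with an event that fits the timing of the infusion, and that also has an identified alternative explanation, is told by one section that it is a drug reaction and by the other that it cannot be rated *Yes*. The same investigator cannot properly rate it *No* either.

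At stake is the consistency of the related-event tables, which are a main summary of ANV419 toxicity, and the input to the pause rule. If sites resolve the gap differently, the related counts partly reflect how each investigator read 7.1.3.

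**Working it through.** The plan states no figure here, so the check is logical. Each definition joins two conditions with *and*: a timing condition and an other-cause condition. Crossing them gives four combinations.

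| Timing | Other cause | Meets *Yes* in 7.1.3? | Meets *No* in 7.1.3? | Result |
|---|---|---|---|---|
| Consistent | None identified or suspected | Yes | No | *Yes* |
| Excludes causality | Suspected | No | Yes | *No* |
| Consistent | Identified | No: another cause is identified | No: timing does not exclude causality | Unassigned |
| Excludes causality | None suspected | No: timing is not consistent | No: no other cause is suspected | Unassigned |

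Two of the four combinations have no category.

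**Conflict with 7.1.1.** Take the third row. Timing is consistent and an identified alternative does not by itself exclude the drug, so the event can satisfy the 7.1.1 test, "ie, the relationship cannot be ruled out". It nevertheless fails *Yes* in 7.1.3. It also sits badly with the *Yes* label, since a drug that is one of two candidate causes is an ordinary example of a possible relationship.

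**Identified or suspected.** *Yes* is defeated by a cause that can be identified; *No* asks for one that is suspected. Neither word is defined. With consistent timing and an alternative that is merely possible, *Yes* may or may not be open. The gap is therefore certain for an identified alternative and ambiguous for a possible one.

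**What follows from each entry.** For a third-row event:

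- Recorded as *Yes*: it enters the related tables and can trigger the pause if it meets the 4.3.1 criteria.
- Recorded as *No*: it leaves the ANV419-related tables, and the pause applies only if the SRC judges the event related.
- Left blank: SAP 3.8.1 counts it as related in the tables.

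Nothing in either document tells the investigator which entry to make. The labels pull in opposite directions: *Yes* takes in possible relationships, while *No* takes in unlikely ones.

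**The case against.** The strongest reply is that 7.1.3 should be read as a whole. The *Yes* label includes possible relationships, the sentence after the definitions brings back a reasonable possibility, other causes are listed as factors to weigh, and the SAP uses a reasonable causal relationship. An investigator reading it this way would apply the 7.1.1 standard. That is a fair reading and some sites may have followed it. But it sets aside an explicit condition in the definition, and no text says that the condition yields.

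A reader might infer that the wording systematically under-counts drug-related toxicity and that a pause could be missed as a result. The documents do not support this:

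- Read literally, third-row events are unassigned, not unrelated. Rating them *No* would breach the *No* definition as well.
- A blank is counted as related in the tables (SAP 3.8.1).
- Under 4.3.1 the SRC's own judgment is enough to trigger the pause, and Protocol 4.3 bases suspension on regular review of SAEs without a relatedness condition.
- SAEs within the reporting window go to the safety group within 24 hours whatever their cause (Protocol 7.3), as do AESIs (Protocol 7.1.4).
- TEAEs and serious TEAEs are tabulated regardless of attribution (SAP 3.8.1.1), so total toxicity stays visible.
- Expedited reporting in Protocol 7.5 concerns suspected adverse reactions, and 7.1.1 defines a reaction by the broad standard.

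Nor do the documents show that events with a competing cause are the usual case in this population. Protocol 5.4.5.4 does say that attribution to one component will be difficult, but it speaks of the combination arms, which were not run.

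These safeguards limit the harm. They do not supply the missing categories or make the related-event tables consistent.

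**Conclusion.** The point holds as a defect in a stated rule. The two categories in 7.1.3 are not exhaustive, and the *Yes* condition contradicts 7.1.1 for events with consistent timing and an identified alternative cause. That part follows from the text and needs no assumption beyond reading *and* as *and*. For alternatives that are only possible, the text is ambiguous.

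The consequence is conditional. Ratings may vary between investigators, and an event drops out of the related tables only where *No* was actually recorded because of another cause. How often that happened, and whether the net effect raises or lowers the related counts, cannot be derived from the documents.

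SAP sections 1 and 5 record that the trial stopped after Part 1 and that no Part 2 or Part 3 analyses will be done. The practical effect is therefore confined to the Part 1 safety results.

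**What to change.** Reconcile 7.1.3 with 7.1.1 so that every adverse event falls in exactly one category:

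- *Yes*: there is a reasonable possibility of a causal relationship (it cannot be ruled out), whether or not another cause is also possible.
- *No*: there is no reasonable possibility of a causal relationship.

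The listed factors can stay as considerations in reaching that judgment. The cost is a change of wording in the protocol and the eCRF guidance. The downside is that some more events may be rated related.

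For the completed Part 1 data, the clinical study report should state which causality definition was applied and present all-causality results alongside the related-event tables. SAP 3.8.1.1 already plans the all-causality summaries, so this needs no new analysis.
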